The above data demonstrate: (1) our ability to enroll and retain HCV-infected IDUs; (2) efficacy of enhanced mDOT v. standard mDOT; and (3) promising early outcomes with telaprevir-based therapy. However, because this pilot RCT was not powered to demonstrate increased SVR with mDOT (and both arms included some degree of DOT), we now propose a definitive study to determine if DOT is associated with increased SVR for genotype-1 patients, and whether DOT is cost-effective.¹²⁹ We will have sufficient power to answer this question as treatment for genotype-1 patients is more effective (SVR=75%),⁴⁶ we will include only genotype-1 patients, and all medications will be self-administered in the proposed TAU arm.

D.1.5. Concurrent Group Treatment (CGT). In 2009, we implemented a group treatment model of HCV care. To date, 39 patients have initiated CGT (including 34 enrolled in the mDOT study described above). Early treatment outcomes are promising, with 89% of patients completing at least 80% of planned treatment duration, and only 2 patients discontinuing treatment because of side effects. Of the first 20 patients who initiated CGT, 80% achieved an end of treatment response and 55% achieved SVR, including 57% of those

with genotype-1 (half active drug users).¹³⁰ Eight CGT patients have initiated telaprevir-based regimens, 7 of 8 had 4 week HCV VL <43 IU, 5 out of 8 had undetectable VL, with one discontinuing treatment. These data demonstrate that CGT is a promising model of care for treating IDUs. However, since patients were not randomized, it is possible that CGT patients were more motivated than others. The 2 x 2 figure demonstrates the effects of each intervention (mDOT and CGT), as well as of their interaction. When

subjects were treated individually with mDOT, or when the subjects were treated with CGT (without mDOT), adherence and virological outcomes were better than without either intervention. However, the additive effects of mDOT and CGT appear modest. For this reason, as well as to increase generalizability, in the proposed study we will evaluate 2 models of intensive care: mDOT (both IFN and oral medications) and CGT (IFN directly-administered and oral meds self-administered). Both models must be rigorously tested to determine whether intensive models of care are superior to standard on-site care for achieving SVR.

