D.1.8. Cost pilot data. Drs. [name] and [name] conducted a retrospective chart review of costs of HCV treatment for patients treated in a methadone maintenance program. Mean treatment costs were \$40,600 for patients with SVR and \$31,400 for patients without SVR. Drs. [name] and [name] conducted a study of health care services utilization by HCV-infected patients in the AIDS Clinical Trials Group Longitudinal Linked Randomized Trials Cohort¹³⁶ in which they described the additional use of hospital and emergency department services associated with HCV infection in this cohort after adjusting for demographic and clinical factors. [name] has also assessed the cost of HIV medication adherence support interventions.¹³⁷

D.2. Overview of study approach. In the proposed study, 150 HCV-monoinfected IDUs (genotype 1) eligible for on-site HCV treatment will be recruited from opiate agonist treatment clinics and randomized to one of 3 models of care: modified directly observed treatment (mDOT); concurrent group treatment (CGT); or standard on-site treatment which represents the treatment as usual arm (TAU). We will compare the proportion of patients in each arm who optimally adhere (>80%), complete treatment, achieve SVR, and develop resistance. We hypothesize that both intensive models of care (mDOT and CGT) will be superior to TAU. Participants on 48 week regimens (e.g. telaprevir) will be followed for 72 weeks (up to 48 weeks of HCV treatment + 24 weeks of follow-up), with visits occurring every 4 weeks for the first 24 weeks, followed by 4 additional visits at 12 week intervals. Participants (n=100) on 12 – 24 weeks regimens (fixed-dose ledipasvir and sofosbuvir) will be followed up to 48 weeks (up to 24 weeks of HCV treatment + 24 weeks of follow-up) with visits occurring every 4 weeks for the first 12 weeks, week 24 (if necessary), end of treatment, and follow-up weeks (4, 12 and 24). Data sources will include blood tests (HCV viral load and resistance tests), urine toxicology tests, questionnaires, medical records, electronic monitors for assessing adherence, and staff logs and direct observation (for cost-effectiveness analysis). In pooled analyses of all subjects (n=150), we will determine associations between adherence and development of resistance. We will also assess cost and cost-effectiveness of all 3 models.

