D.11. Analytic plan. First, the success of randomization will be checked by comparing the mDOT, CGT and TAU groups on key variables, such as age, gender, ethnicity, race, HCV viral load, HCV subtype (1a vs. 1b), BMI, psychiatric history, active drug use, and social support.⁴⁶ By design, IL28B and stage of liver disease will be represented equally in each arm. Continuous variables will be compared between arms using the ANOVA or Kruskal-Wallis test, and categorical variables will be compared using chi-square or Fisher's exact tests. Variables that are not equally distributed will be included in multivariate models. In primary analysis, we will use the intention-to-treat principle, which preserves the advantages of a randomized design.

D.12.1. Hypotheses for Aim 1. We hypothesize that in the intensive intervention arms, compared to the control arm, rates of adherence, treatment completion, and SVR will be significantly higher, and that rates of resistance will be lower. We further hypothesize that the proportion of subjects in the intensive models of care arms who achieve an SVR will be equivalent to that observed in large registration trials.

D.12.2. Analytic plan for Aim 1. Adherence to DAAs, ribavirin, and IFN will be determined using electronic monitors and self report, as described above. Initially, adherence will be calculated as a single outcome for each subject, evaluated at the end of the study. We will use Chi-square tests or Fisher's exact test to compare the proportion of subjects who achieve high adherence rate ($\geq 80\%$) complete treatment, achieve SVR, and develop resistance in the three arms (mDOT, CGT, and TAU). If the omnibus equality test of adherence across the 3 groups is rejected, we will conduct the following 2 specific post-hoc pairwise tests with a Bonferroni adjusted 2-sided alpha= 0.025: mDOT vs. control, and CGT vs. control. This strategy will be applied to multivariable logistic regressions if any potential confounding variables not equally distributed between the study arms at baseline are identified.

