We will use the model to assess the cost-effectiveness of the 3 interventions: TAU, mDOT, and CGT. Primary outcomes will be projected life-expectancy, quality-adjusted life-expectancy (QALYs), lifetime costs, and incremental cost-effectiveness ratios measured in \$/QALY. We will forecast health and cost outcomes of each intervention for a hypothetical cohort of HCV patients using baseline study data on fibrosis, age, sex, and alcohol use, and study outcome data for each intervention including SVR, resistance, and retention in care. We will explore the potential impact of resistance mutations by varying the efficacy of subsequent HCV retreatment for patients with resistance who choose to be retreated. Lifetime costs will include the costs of the intervention received as well as projected future costs of HCV care depending on treatment effectiveness. Incremental cost effectiveness ratios will be calculated for TAU compared to no treatment and for mDOT and CGI compared to the next most expensive intervention, with costs and QALYs discounted at 3% annually according to standard practice.¹⁷³ The resulting ratios will be compared to a threshold of \$100,000 per QALY.¹⁷⁴⁻¹⁷⁵ To explore uncertainties in our results, we will perform one and 2-way sensitivity analyses on key input variables (e.g. probability of SVR and intervention cost) and probabilistic sensitivity analyses (PSAs) using second order Monte Carlo simulation on multiple variables.¹⁷⁶ For PSAs we will perform 1,000 simulations of a cohort of 100,000 individuals. The result will be a distribution of 1,000 model-based outcomes with a median and interquartile range that reflects underlying uncertainty in critical model parameters.

D.13 Power considerations Assuming a conservative attrition rate of 20%, 50 subjects per arm will begin the study, but 40 subjects per arm will complete it. For power calculations for repeatedly measured continuous or binary adherence outcomes, we will use the expected number of observations per subject. The power analysis is conducted based on the omnibus testing of equality across the three groups. It follows that at least one of the post-hoc pair-wise tests is powered to be rejected by this study design.

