Adherence. Based on our pilot data, if we conservatively assume that 80% of subjects in both mDOT and CGT arms will achieve $\geq 80\%$ adherence (v. 50% in the TAU arm), we will have $> 87\%$ power to find a statistically significant difference. With the application of mixed-effects logistic regression to the repeatedly measured binary adherence outcome, power will be greater than 87% no matter how large the within-subject outcome correlation or intraclass correlation (ICC).

In our previous DOT study, mean adherence in the mDOT group was 87% (SD=12%, n=21), and mean adherence in the TAU group was 77% (SD=20%, n=19) which translates into a standardized effect size or Cohen's $d = 0.6$. Based on this effect size, the power of the mixed effects linear model for the repeatedly measured continuous adherence outcome will be greater than 90%, even if anticipated ICC is as high as 0.5.

Treatment completion. Based on our pilot data, if we assume treatment completion rates of 85% in CGT, 60% in mDOT, and 50% in TAU, we will have $> 80\%$ power to detect this difference.

SVR. We anticipate that SVR rates in the mDOT and CGT arms will be 70%, and $\leq 40\%$ in the TAU arm.^{13,70,82} The statistical power will be $> 80\%$. These are conservative estimates of effect sizes, as actual effect sizes will likely be larger because regimens now contain telaprevir which is taken 3x daily. Effects size for fixed-dose (ledipasvir and sofosbuvir) is likely to be lower.

Resistance. We estimate that 16% of intervention arm subjects v. 30% of TAU subjects will develop resistance. We are underpowered to detect this difference, and consider this an exploratory analysis.

Effectiveness of intensive models of care. We will determine the proportion (and 95% CI) of subjects in each of the intensive intervention arms to achieve SVR, and compare to results from large registration trials.

D.14. Limitations. In addition to the considerations noted in Section D., our results may not be generalizable to HCV-infected drug users not enrolled in methadone clinics. However, we believe that the intensive models we are testing, if efficacious, can and should be adopted in diverse settings and populations.

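### D.13's power figures hold for the three-arm omnibus test but not for each model's own comparison with TAU: mDOT v TAU has about 9% power on completion and, at 70% v 40%, about 68% on SVR

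*Combined protocol and SAP*

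**What the plan says.** D.13 sets the basis for all its power figures: "The power analysis is conducted based on the omnibus testing of equality across the three groups". It assumes 50 enrolled and 40 completing per arm, and then draws one inference about the pairwise tests: "It follows that at least one of the post-hoc pair-wise tests is powered to be rejected by this study design". For completion it claims more than 80% power "if we assume treatment completion rates of 85% in CGT, 60% in mDOT, and 50% in TAU". For SVR it claims more than 80% with 70% in both intensive arms and at most 40% in TAU. For adherence it claims more than 87% with 80%, 80% and 50%. No power is given for any single comparison.

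Other sections ask questions about each model. The last paragraph of D.1.4 presents the trial as the definitive test of whether DOT raises SVR and adds: "We will have sufficient power to answer this question". D.2 says: "We hypothesize that both intensive models of care (mDOT and CGT) will be superior to TAU". D.12.2 plans "2 specific post-hoc pairwise tests with a Bonferroni adjusted 2-sided alpha= 0.025: mDOT vs. control, and CGT vs. control". The condition for that step is worded for one outcome only: "If the omnibus equality test of adherence across the 3 groups is rejected".

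**The concern.** The omnibus test asks whether the three arms differ at all. It does not say which model works. A large effect in one arm can carry it while the other model's comparison has almost no power. The completion assumptions have this shape: CGT is 35 points above TAU and mDOT is 10 points above.

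Two things are at stake. A non-significant mDOT result on completion could be read beside a figure of more than 80% and taken as evidence that DOT does not help, although the design would usually miss the effect the plan itself assumes. The D.1.4 claim about DOT and SVR, and the D.2 hypothesis about both models, also need pairwise or joint power, and the plan reports neither. D.13 is open about this for resistance, which it calls underpowered and exploratory, but says nothing of the kind about mDOT on completion.

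**Working it through.** **Inputs.** From D.13: 40 completers per arm; completion 85% CGT, 60% mDOT, 50% TAU; SVR 70/70/40 (40% is the plan's upper bound for TAU); adherence 80/80/50. From D.12.2: pairwise two-sided alpha 0.025. The omnibus alpha is not stated; 0.05 is assumed. The 0.025 step is extended from adherence to completion and SVR.

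**Step 1: reproduce the plan's figures.** For a 2-df chi-square test, λ = n·Σ(pᵢ − p̄)² / [p̄(1 − p̄)], and power is the chance that a noncentral chi-square with that λ exceeds 5.991.

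- Completion: p̄ = 0.65; λ = 40 × (0.04 + 0.0025 + 0.0225) / 0.2275 = 11.43; power 86.7% (simulated 89.9%). Stated: more than 80%.
- SVR: p̄ = 0.60; λ = 40 × (0.01 + 0.01 + 0.04) / 0.24 = 10.0; power 81.5% (simulated 82.1%). Stated: more than 80%.
- Adherence: p̄ = 0.70; λ = 40 × 0.06 / 0.21 = 11.43; power 86.7% (simulated 86.3%). Stated: more than 87%, a rounding-size difference.

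The stated figures are therefore omnibus powers.

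**Step 2: each comparison with TAU.** Power = Φ[(d − z·s₀)/s₁], with z = 2.2414 for two-sided 0.025, s₀ = √[2p̄(1 − p̄)/n] and s₁ = √{[p₁(1 − p₁) + p₂(1 − p₂)]/n}, where p̄ is now the mean of the two arms.

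- Completion, mDOT v TAU: (0.10 − 2.2414 × 0.1112)/0.1107 = −1.35; power 8.9%.
- Completion, CGT v TAU: (0.35 − 2.2414 × 0.1047)/0.0971 = 1.19; power 88.2%.
- SVR, either model v TAU: (0.30 − 2.2414 × 0.1112)/0.1061 = 0.48; power 68.4%.
- Adherence, either model v TAU: (0.30 − 2.2414 × 0.1067)/0.1012 = 0.60; power 72.6%.

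**Step 3: the full procedure** (omnibus at 0.05, then pairwise at 0.025; 400,000 simulated trials, 40 per arm).

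| Outcome | Omnibus | mDOT v TAU | CGT v TAU | At least one | Both |
|---|---|---|---|---|---|
| Completion 85/60/50 | 90% | 9% | 87% | 87% | 9% |
| SVR 70/70/40 | 82% | 68% | 68% | 81% | 55% |
| Adherence 80/80/50 | 86% | 73% | 73% | 85% | 61% |

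On completion, at-least-one power is 87.0% and CGT alone gives 86.9%, so mDOT adds about 0.1 point.

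**Step 4: sensitivity.**

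- mDOT completion: 7% with Fisher's exact test at 40 per arm; 10% with 50 per arm; 14% (two-arm formula) at alpha 0.05 with 40; up to 18% at alpha 0.05 with 50. For 80% power at 0.025, 470 evaluable per arm would be needed.
- SVR, each model: 64% with Fisher's test; 78% with 50 per arm; 78% (two-arm formula) at alpha 0.05 with 40; 85% at alpha 0.05 with 50. At 40 per arm and 0.025, 70% v 36% gives 80%, 70% v 35% gives 83%, and 75% v 40% gives 84%.
- Adherence, each model: 83% with 50 per arm.
- Comparator: resistance at 16% v 30% has about 22% power per comparison at 0.025 with 40 per arm (two-arm formula). D.13 calls that outcome exploratory, yet mDOT completion has less power.

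**The case against.** The strongest reply is that D.13 contains no arithmetic error and hides nothing. It names the omnibus basis, its figures reproduce for that test, and it claims only that at least one pairwise comparison is powered, which holds. A reader might infer that the powers were miscalculated, or that D.13 promises more than 80% for mDOT v TAU on completion. Neither is supported: the completion sentence describes a three-arm pattern, after the omnibus basis has been set.

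The hypotheses are also mixed. The introduction and Aim 1 speak of either model being better than standard care, and on one reading at-least-one power is then the right quantity. D.2 asks for both, and D.12.2 tests each. D.12.2 also writes the 0.025 step for adherence only. Extending it is the natural reading, because the preceding sentence lists all four outcomes together; without the extension, the plan would specify no pairwise chi-square or Fisher test of either model on completion or SVR.

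A reader might also infer that the trial cannot answer the DOT question on SVR. That goes too far. D.13 gives 40% as a ceiling for TAU, D.1.4 cites an SVR of 75%, D.11 makes the primary analysis intention-to-treat (which favours counting all 50 per arm), and D.1.4 attaches no percentage to its claim. Several of these inputs bring power to 80% or above. Against that, 40% is the rate at which the stated SVR power is close to its 80% threshold, and D.13 itself expects a smaller effect with ledipasvir and sofosbuvir, the regimen planned for 100 of the 150 participants.

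None of this rescues mDOT on completion.

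**Conclusion.** The point holds as a mismatch between the power reported and the comparisons that decide each model. It is not a calculation error.

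- **Completion** is the firm part. The power above 80% belongs to the omnibus test and to CGT v TAU. mDOT v TAU has about 9%, and no variant examined exceeds 18%.
- **SVR** depends on assumptions. At D.13's own 70% v 40% with 40 per arm, each model has about 68% and both together 55%. With more favourable inputs, power for each model runs from about 78% to 85%. The D.1.4 claim is unsupported as written because it states neither a figure nor the assumptions it needs.
- **Adherence** is milder: about 73% for each model (83% with 50 per arm) and 61% for both.

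These figures rest on an omnibus alpha of 0.05, which the plan does not state, and on applying the 0.025 step beyond adherence.

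**What to change.** In D.13, label the existing figures as omnibus power and state the omnibus alpha. Beside each, give the power of mDOT v TAU, of CGT v TAU and of both, at the D.12.2 alpha, as ranges over 40 to 50 per arm:

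- Completion: 9–10%, 87–94% and 9–10%.
- SVR at 70% v 40%: 68–78% for each model and 55–66% for both, with further values for TAU rates below 40%, and a note that D.13 already expects a smaller SVR effect with ledipasvir and sofosbuvir.
- Adherence: 73–83% for each model and 61–74% for both.

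Limit the completion claim of more than 80% to the omnibus test and CGT v TAU. Label mDOT v TAU on completion exploratory, reported with a confidence interval, in line with D.13's treatment of resistance. In D.1.4, replace the sufficient-power sentence with the mDOT v TAU SVR power range and its assumptions. In D.12.2, say whether the 0.025 step applies to completion and SVR.

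The cost is rewording only: no more patients and no change in conduct. The downside is that the stated power looks less favourable.

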D.1.3. Study of HCV treatment in methadone patients. In 2003, we adapted our on-site multidisciplinary HCV program to include directly-administered weekly IFN in addition to screening, assessment of treatment eligibility, psychiatric services, and on-site antiviral therapy.⁷⁹ Of 73 patients, most were Latino (67%) or African-American (12%), nearly half (49%) had used illicit substances in the 6 months before initiating treatment, 32% were HIV-infected, and current psychiatric illness was common (67%). Most (86%) completed 12 weeks of HCV treatment and 45% achieved SVR, including 40% of genotype-1 patients. Though 30% used illicit drugs during HCV treatment, there was no association between illicit drug use and virological outcomes. These results demonstrate that IDUs with complex medical and psychiatric comorbidities can be effectively treated for HCV with co-located on-site care. However, it is unknown which interventions (multidisciplinary on-site care v. DOT injections) contributed to the observed outcomes.⁷⁸⁻⁸⁰

D.1.4. Pilot RCT of directly observed HCV treatment in methadone patients. In 2008 we began a pilot RCT (K23 DA022454, PI: [name]) of modified DOT (mDOT) which extended our DOT strategy to the oral medication ribavirin. We designed this trial to test the efficacy of 2 versions of mDOT. Our primary objective was to determine whether enhanced DOT with both IFN plus ribavirin is more efficacious than standard DOT with weekly provider-administered IFN and self-administered ribavirin for improving adherence. We have completed enrollment (n=80), with 74 initiating HCV treatment. We observed significant differences in pill count adherence between the treatment arms (88% in mDOT arm vs. 77% in the treatment as usual, or TAU arm, p=0.02).¹²⁹ In addition, 81% of mDOT subjects achieved ≥ 80% adherence v. 53% in the TAU arm (p=0.09). Only 16% discontinued treatment, and among genotype-1 infected patients (n=22), 55% achieved SVR (half active drug users).¹²⁹ Of the 1st 4 subjects on telaprevir-based triple therapy randomized to DOT, pill count adherence at 4 weeks was 98%, and 3 of 4 had 4 week VL<43 IU/ml, with one subject discontinuing treatment.

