FREQUENCY OF CGT CYCLES. New cycles begin at each of 3 sites 3 times per year; therefore there is a new cycle starting nearly every month. To facilitate rapid entry into a group, trial subjects may elect to wait until a cycle is starting at their “home” clinic site, or travel to a different site. In addition, they may join a group that is already in its first month. (Appendix C for group treatment protocols)

D.9. Specific study design considerations.

D.9.2. Why not include an off-site treatment by referral arm? Our study is urgently needed because off-site referral is the current prevailing model of HCV care, and alternative approaches are needed. [name] has studied outcomes from Montefiore’s liver clinic and found that only 15% were eligible for HCV treatment, and SVR rates for genotype-1 were 14% (compared to 40% in our on-site cohorts).¹³ These suboptimal outcomes on referral from our methadone clinics to our liver clinic motivated us to develop our on-site treatment program, in collaboration with [name].

D.9.3. Why another study of DOT for HCV treatment? To date, no HCV DOT study has demonstrated improved virological outcomes, the most important clinical outcome. Our currently funded study has a heterogeneous population and was powered for adherence, not virological outcomes. This study demonstrates that there is increased adherence with DOT and is the foundation for the proposed trial.

D.9.4. Why use weekly blister packs instead of the standard packaging? Weekly pill boxes and blister packs have been shown to be associated with increased adherence and improved virological outcomes.¹⁴⁷⁻¹⁴⁹ The proposed design will maximize adherence in the control arm and eliminate the chance that suboptimal packaging could be responsible for any effect of the intensive interventions. Since any increase in adherence from blister packaging will be observed in all three arms, it will not contaminate intervention effects.

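### The adherence power in D.13 is called conservative, but it assumes a wider gap (80% v 50%) than the pilot found (81% v 53%); power is about 86% as assumed and about 83% at the pilot rates, not above 87%

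*Combined protocol and SAP*

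**What the plan says.** D.13 (Adherence) derives its rates from the pilot: "if we conservatively assume that 80% of subjects in both mDOT and CGT arms" will reach the 80% adherence threshold, "v. 50% in the TAU arm), we will have" power above 87%. It extends the figure to the repeated binary outcome: "power will be greater than 87% no matter how large the within-subject outcome correlation". The opening paragraph of D.13 sets 50 starters and 40 completers per arm after 20% attrition, and bases power on the omnibus comparison of the three arms.

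The pilot result is in D.1.4: "81% of mDOT subjects achieved ≥ 80% adherence v. 53% in the TAU arm (p=0.09"). No CGT rate on this threshold is reported.

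D.12.2 compares the three proportions by chi-square or Fisher's exact test. If the omnibus adherence test rejects, mDOT and CGT are each compared with control at a two-sided 0.025. No alpha is stated for the omnibus test.

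**The concern.** A conservative planning value is no more favourable than the evidence it comes from. Here the intensive-arm rate was moved 1 point against the hypothesis (81% to 80%) and the control rate 3 points in its favour (53% to 50%). The net effect is a wider gap than the pilot showed, described as a cautious one.

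The power figure is also given as a strict lower bound, and then as a bound that holds at any within-subject correlation. If it is missed at the assumed rates, both statements need correcting. Rejecting the omnibus adherence test opens the two pairwise comparisons in D.12.2, so its power should be stated accurately.

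**Working it through.** **Inputs.** Planned rates 80/80/50 (mDOT/CGT/TAU) and n = 40 per arm come from D.13. Pilot rates of 81% and 53% come from D.1.4. The mDOT rate is used for CGT as well, because D.13 also gives the two intensive arms one common rate. Omnibus alpha 0.05 is an assumption.

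**Formula.** Pearson chi-square on 2 degrees of freedom, critical value 5.99. The noncentrality is λ = n·Σ(pᵢ − p̄)² / [p̄(1 − p̄)], and power is the upper tail of the noncentral chi-square. With two equal intensive arms and a gap d to TAU, the sum of squares is (2/3)d².

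**The plan's own case, 80/80/50.**
- p̄ = (0.80 + 0.80 + 0.50)/3 = 0.70
- sum of squares = (2/3)(0.30)² = 0.0600
- λ = 40 × 0.0600 / (0.70 × 0.30) = 11.43
- power 86.6%; exact enumeration of the same test gives 86.3%

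The stated figure is therefore reproduced to within a point, but the strict bound of 87% is narrowly missed.

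**Pilot rates, 81/81/53.**
- p̄ = 2.15/3 = 0.7167
- sum of squares = (2/3)(0.28)² = 0.0523
- λ = 40 × 0.0523 / (0.7167 × 0.2833) = 10.30
- power 82.7%; exact 82.3%

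**No more favourable than the pilot in any arm, 80/80/53.** λ = 40 × (2/3)(0.27)² / (0.71 × 0.29) = 9.44, power 79.1%. This is what the label would have meant if applied to both rates.

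**Repeated binary outcome.** As the within-subject correlation approaches 1, further visits add no information and the analysis has only the single-outcome power. A bound that holds for every correlation therefore cannot exceed the single-outcome figure: about 86% at the planned rates and about 83% at the pilot rates.

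**Sensitivity to the TAU rate.** Intensive arms are held at 81%, n = 40. TAU rates other than 53% are assumptions.

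| TAU rate | λ | Power |
|---|---|---|
| 45% | 16.16 | 96% |
| 50% | 12.36 | 89% |
| 53% | 10.30 | 83% |
| 55% | 9.01 | 77% |
| 60% | 6.11 | 59% |

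Power moves by 6 points either way when the TAU rate falls by 3 points or rises by 2, so the choice of this rate needs a stated reason.

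**The case against.** The best defence is that the pilot control arm is not the trial's control arm. In D.1.4 the pilot TAU arm had provider-administered interferon. D.1.5 says that 34 of the CGT patients were enrolled in the pilot, and the accompanying 2 x 2 table shows 4-week adherence in TAU of 92% with CGT (n=11) against 68% without (n=14). The trial's TAU arm is to be fully self-administered (D.1.4) and has no group treatment. A rate below 53% is therefore arguable, and 81/81/50 would give 89%. This stands as a possible justification. D.13 does not offer it, however: it attributes the rates to the pilot and calls them conservative.

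It is also fair that the pilot gap is imprecise. If the arm sizes of 21 and 19 quoted in D.13 apply (an assumption), 17/21 v 10/19 reproduces p = 0.09 by Fisher's test. The approximate 95% interval for the gap is then 28 ± 28 points, or about 0 to 56. A difference of 28 v 30 lies well inside that. The pilot adherence in D.1.4 is by pill count and the trial's by electronic monitor, and no CGT rate on this threshold exists. So 83% is not the true power. It is what the cited evidence yields, and its imprecision is a reason to show a range.

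A reader might go further and infer from D.9.4 that blister packs will cut the power, since "The proposed design will maximize adherence in the control arm". The documents do not support that. The same section expects any packaging gain in all three arms, gives no size for it, and the documents do not say how pilot pills were packaged. An equal gain would raise power: 86/86/58 keeps the 28-point gap and gives 87.4%. Power falls only if TAU gains more than the other arms.

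**Conclusion.** The point holds as a minor correction. The 30-point planning gap is wider than the 28-point pilot gap, so *conservatively* is unsupported as written. Power is about 86.5% at the planned rates, under one point short of the stated bound, and about 83% at the pilot rates, roughly 4 points lower. The guarantee at any within-subject correlation is limited to the same figures.

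This rests on 40 per arm, an omnibus alpha of 0.05 and a common rate for mDOT and CGT. It does not show that the trial is underpowered for adherence: omnibus power at the pilot rates remains above 80%. Nor is this figure the only support for the sample size, since D.13 also claims more than 90% for continuous adherence and more than 80% each for completion and SVR; those claims are not examined here.

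**What to change.** In D.13 (Adherence):

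1. Delete *conservatively*, or keep 50% for TAU and justify it explicitly from the directly observed and group-treatment content of the pilot TAU arm.
2. State the omnibus alpha, and give power as about 86% at 80/80/50 and about 83% at the pilot rates, in both the single-outcome and the repeated-measures statements.
3. Add one line, labelled as assumptions, with the intensive arms at 81%: TAU 45% = 96%, 50% = 89%, 53% = 83%, 55% = 77%, 60% = 59%.

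No new data and no design change are needed. The cost is a slightly less favourable stated figure.
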